476 experience. This will examine relevant core constructs of trust, acceptance, satisfaction,
477 confidence as well as fear, worries, distress and burden. Validated and reliable measures will be
478 used to explore psycho-behavioral characteristics and outcomes in addition to specifically
479 adapted measures for SAM and DSS technologies to capture holistic, disease-specific and
480 technology-specific data. These questionnaires will evaluate how specific constructs are
481 predictive of successful glycemic outcomes associated with DSS. These questionnaires will enable
482 us to assess important non-glycemic treatment outcomes that are meaningful to patients
483 including those affecting Quality of Life (QOL) (e.g. fear of hypoglycemia and diabetes distress).
484 To those ends, participants will complete a battery of questionnaires related to diabetes
485 management, treatment satisfaction and QOL at baseline (before system use) and after each
486 treatment modality.

487 **1.3.5. Ecological Momentary Assessment Data Collection**

488 Participants will be trained on the EMA surveys and requirements. During each treatment
489 condition, over the course of 2-3 days every two weeks, the participant will be asked to complete
490 a "Daily Diary" with 3-5 entries of 3-4 questions each day, for a minimum total of 48 entries per
491 participant during each Phase. The DiAs phone will display a text message containing a link to the
492 survey. Surveys will be triggered at fixed times, including a morning survey ~1h after waking up
493 and an end-of-the-day survey around 8-9 PM. Participants will be able to delay (up to 30 min) or
494 skip (up to 2 per day excluding at wake up) surveys for their convenience. Participants will
495 respond to questions on a 5-point Likert scale (0=Not at All, 4=Extremely). The first Diary for each
496 day will contain two additional items for rating sleep quantity/quality. The Daily Diary questions
497 are intended to assess agreement, trust, treatment satisfaction, diabetes burden, self-efficacy,
498 mood valence, energy level, physical well-being, and concerns about hypo- and hyperglycemia.
499 The first Diary for each day will contain two additional items for rating sleep quantity/quality.

CLINICAL PROTOCOL

500 **1.3.6. Mapping of Psycho-behavioral Characteristics to DSS Preferences and Performance**

501 Baseline assessments of psycho-behavioral traits will be introduced as covariates in the general

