800 An appointment for Visit 3 will be scheduled.

801 **5.2.2. Questionnaires**

802 Participants will be sent the following questionnaires on the final week of the Run-in Period and
803 will be asked to complete them within 1 week:

- 804 • T1-Diabetes Distress Scale
- 805 • Hypoglycemia Fear Survey

CLINICAL PROTOCOL

- 806 • Hyperglycemia Avoidance Scale

807 **5.3. Visit 3 – Eligibility Assessment, Randomization and Training**

808 The participant may complete this visit via web conferencing and/or at the study site.

809 **5.3.1. Eligibility Assessment**

810 The CGM and insulin data will be reviewed to assess whether the subject has used the DiAs
811 system in SAM on at least 11 out of 14 days for CGM users or 22 out of 28 days for non-CGM
812 users. Subjects who are unable to meet the CGM and DiAs compliance requirement will be
813 withdrawn from the study, unless the investigator believes that there were extenuating
814 circumstances that prevented successful completion. In such cases, the investigator may ask the
815 participant to repeat this eligibility assessment.

816 **5.3.2. Adverse Event Assessment**

817 The participant will be asked about any of adverse events, adverse device effects, and device
818 issues since the last visit. The participant will also be asked if there were any low BGs <54 mg/dL,
819 high BGs >300 mg/dL, or ketones ≥ 3.0 mmol/L since the last visit. Participants will be encouraged
820 to contact the study team between visits as needed (i.e. report adverse events in real-time).

821 **Chapter 6 Study Procedures - Escalation**

822 **6.1.1. Randomization to Escalation**

823 Eligible subjects will be randomized to therapy escalation (SAM→PF→DSS).

824 A baseline Hemoglobin A1C will be collected. The participant will receive a mode change for
825 Phase 1 according to the randomization scheme.

826 **6.2. Sensor Augmented Mode**

827 Participants randomized to escalation will have any questions answered about continuing use of
828 the DiAs system in SAM.

829 **6.2.1. SAM EMA Surveys**

830 Over the course of 2-3 days every two weeks of Phase 2, the participant will be asked to complete
831 a “Daily Diary” with 3-5 entries of 3-4 questions each day, for a minimum total of 48 entries per
832 participant during each Phase.

833 **6.2.2. Phase 1 Initiation Questionnaires**

834 Participants randomized to escalation will complete the following questionnaires:

- 835 • Pittsburgh Sleep Quality Index

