980 **7.1. Randomization to De-Escalation**

981 Eligible subjects will be randomized to therapy de-escalation (DSS→PF→SAM).

982 A baseline Hemoglobin A1C will be collected.

983 The participant will receive a mode change for Phase 1 according to the randomization scheme.

984 **7.2. Training on Phase 1 DiAs Mode**

985 Participants randomized to de-escalation will be trained to use DiAs in DSS mode, including the
986 following features:

- 987 • **Exercise Advice:** An advisory module that ensures safety of mild to moderate exercise by
988 predicting whether an exercise bout is likely to result in hypoglycemia and providing a
989 graded carbohydrate supplementation strategy and possible reduction in insulin advice.
- 990 • **Bedtime Advice:** Gauges overnight hypoglycemia risk and provides bedtime carbohydrate
991 advice.
- 992 • **Smart Bolus Calculator:** An advanced bolus calculator capable of accounting for several
993 factors such as exercise (activity on board), metabolic characteristics (correction based
994 on 45 min predicted glucose to account for insulin delays) and SI fluctuations (insulin
995 sensitivity tracker).
- 996 • **Treatment Parameter Optimization:** An optimization routine that analyzes the previous
997 30 days of CGM, insulin, and meal data to provide updated insulin treatment parameters
998 (CR, CF, and basal rate) to minimize glycemic risk.

999 **7.2.1. Phase 1 EMA Surveys**

1000 Over the course of 2-3 days every two weeks of Phase 2, the participant will be asked to complete
1001 a “Daily Diary” with 3-5 entries of 3-4 questions each day, for a minimum total of 48 entries per
1002 participant during each Phase.

1003 **7.2.2. Phase 1 Initiation Questionnaires**

1004 Participants randomized to de-escalation will complete the following questionnaires:

- 1005 • Pittsburgh Sleep Quality Index
- 1006 • Technology Expectations (burdens subscale only)
- 1007 • INSPIRE (revised for DSS)

1008 Once all training activities are completed, the participant will be given adequate supplies and
1009 study devices to last until the subsequent clinic visit. An appointment for Visit 4 will be scheduled.

CLINICAL PROTOCOL

1010 **7.3. Home Use of DiAs in Phase 1 Mode**

1011 The participant will complete a minimum of 8 weeks of DiAs use in Phase 1 Mode at home. During
1012 the course of Phase 1, participants will complete EMA surveys and post-phase questionnaires.

1013 **7.3.1. Phase 1 EMA Surveys**

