1014 Over the course of 2-3 days every two weeks of Phase 1, the participant will be asked to complete
1015 a “Daily Diary” with 3-5 entries of 3-4 questions each day, for a minimum total of 48 entries per
1016 participant during each Phase.

1017 **7.3.2. Post-Phase 1 Questionnaires Week 7**

1018 Participants randomized to de-escalation will be sent the following questionnaires on week 7
1019 (day 42 of Phase 1) and will be asked to complete them within 1 week:

- 1020 • Technology Acceptance (burdens subscale only)
- 1021 • Pittsburgh Sleep Quality Index
- 1022 • T1-Diabetes Distress Scale

1023 **7.3.3. Post-Phase 1 Questionnaires Week 8**

1024 Participants randomized to de-escalation will be sent the following questionnaires on week 8
1025 (day 49 of Phase 1) and will be asked to complete them within 1 week:

- 1026 • Hypoglycemia Fear Survey
- 1027 • Hyperglycemia Avoidance Scale
- 1028 • Confidence in Diabetes Self-Care Scale

1029 **7.4. Visit 4 – Phase 2 Initiation**

1030 All participants in each randomization scheme use PF in Phase 2. Phase 2 initiation may be
1031 conducted either via web conference or an office visit. The participant will remotely receive a
1032 mode change for Phase 2. Study staff will review the features of the Personalized Feedback (PF)
1033 mode and answer any questions.

1034 **7.4.1. Training on Phase 2 DiAs Mode**

1035 The participant will be trained on the following features of the Personalized Feedback System:

- 1036 • **Tracking of estimated HbA1c:** When properly calibrated, eA1c is within 0.3% of reference
1037 HbA1c on average, and within 1% of HbA1c >95% of the time.
- 1038 • **Hypoglycemia Risk Indicator:** Provides an indication of the current risk for hypoglycemia.

CLINICAL PROTOCOL

- 1039 • **Insulin Sensitivity Profile & Indicator:** Tracks changes in insulin sensitivity (SI) and creates
1040 daily and monthly SI profiles.
- 1041 • **Insulin on Board:** Tracks active insulin to avoid insulin stacking using a common 4-6 hour
1042 action curve.
- 1043 • **Personalized weekly feedback.** Provides advice to the user on what went well in terms of
1044 glycemic control and system use in the past week and what may be a good thing to focus
1045 on for the following week.

1046 **7.4.2. Phase 2 Initiation Questionnaires**

1047 Participants randomized to de-escalation will complete the following questionnaires:

- 1048 • Technology Expectations (burdens subscale only)
- 1049 • INSPIRE (revised for DSS)

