1213 This measure is used to assess the extent of potentially problematic avoidant attitudes and
1214 behaviors in people with T1DM [91]. The Hypoglycemia Avoidance Scale reliably quantifies
1215 affective and behavioral aspects of hyperglycemia avoidance and is used to assess the extent of
1216 potentially problematic avoidant attitudes and behaviors regarding hyperglycemia in people with
1217 T1DM. It has 24 items plus two additional optional items asking about the highest level of daily
1218 blood glucose or HbA1c measures the individual would feel comfortable having. Administration
1219 time is approximately 10 minutes.

CLINICAL PROTOCOL

1220 **9.9. Pittsburgh Sleep Quality Index**

1221 This questionnaire will be used to assess whether the PF and DSS improve sleep quality and
1222 quantity. The Pittsburgh Sleep Quality Index [93] is a self-report questionnaire that assesses sleep
1223 quality over a 1-month time interval. The measure consists of 19 individual items, creating 7
1224 components that produce one global score: the higher the global score, the poorer the sleep
1225 quality. Administration time is approximately 5-10 minutes.

1226 **9.10. Technology Acceptance and Expectations Survey (burdens subscale only)**

1227 The Technology Acceptance Surveys [94-95] were developed for an artificial pancreas camp study
1228 in adolescents. The 38 items in the questionnaire were based on interviews conducted with
1229 individuals who had participated in previous artificial pancreas trials about their experience
1230 regarding the device. It was subsequently adapted to assess these same measures for the PF and
1231 DSS. It assesses both positive and negative experiences with PF and DSS, including blood glucose
1232 management, device burden, and overall satisfaction. Items are rated on a 5-point scale. In this
1233 study only the burden subscale will be used. The Technology Expectations Survey has the same
1234 items included on the Technology Acceptance Survey but asks whether the individual expects to
1235 experience the various benefits and burdens from use of a device. Administration time is
1236 approximately 10 minutes.

1237 **9.11. INSPIRE (revised for DSS)**

1238 This questionnaire will be used to assess patient preferences to support effective onboarding and
1239 successful continued use of the PF and DSS. The INSPIRE survey was developed to assess various

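### The only sleep-quality score before Phase 1 comes from participants already randomized, and the run-in distress, fear and avoidance forms can be returned after randomization

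*Combined protocol and SAP*

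**What the plan says.** **Sleep form.** The PSQI is in neither the Visit 1 battery (section 3.5) nor the run-in set (5.2.2). It first appears among the Phase 1 initiation questionnaires. For escalation, 6.2.2 introduces them with "Participants randomized to escalation will complete the following questionnaires"; for de-escalation, 7.2.2 uses "Participants randomized to de-escalation will complete the following questionnaires". The table in 9.13 agrees, listing the PSQI first at Visit 3 for both sequences. Its purpose is given in 9.9: "This questionnaire will be used to assess whether the PF and DSS improve sleep quality and" quantity. The same section gives it a 1-month recall period.

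**Allocation.** Section 7.1 covers randomization and the Phase 1 mode change. Section 7.2 then opens with "Participants randomized to de-escalation will be trained to use DiAs in DSS mode, including the" features listed there. On the middle period, 6.4 and 7.4 state: "All participants in each randomization scheme use PF in Phase 2".

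**Run-in forms.** Section 5.2.2 covers the distress, hypoglycemia fear and hyperglycemia avoidance forms: "Participants will be sent the following questionnaires on the final week of the Run-in Period and" are given 1 week to complete them. It names no sending day. Visit 3 is to be scheduled, with no stated interval after run-in. The eligibility check in 5.3.1 reviews device use only.

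**Use of the scores.** Section 1.3.4 plans questionnaires on diabetes "management, treatment satisfaction and QOL at baseline (before system use) and after each" treatment modality. Section 14.5 will look for change in questionnaire scores over time and between groups, with group assignment and study phase as covariates.

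**The concern.** A starting score is useful for comparing randomized groups because allocation cannot have affected it. Here the only PSQI before Phase 1 is requested from people already assigned to a sequence, in an open trial. Someone told they will start DSS, or that they will stay on SAM, may rate their sleep differently because of expectation or disappointment. The companion forms also differ: at Visit 3 the de-escalation group completes the PSQI with two technology forms, while the escalation group completes it alone.

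The three run-in forms are meant to come earlier, but the schedule does not guarantee it. A form returned after Visit 3 could reflect knowledge of the sequence and, in de-escalation, some days on DSS.

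What is at stake is the over-time and between-group analysis in 14.5. With only two sequences, SAM→PF→DSS and DSS→PF→SAM, Phase 1 is the one period in which randomized SAM and DSS groups can be compared before either has been through another randomized mode. If the starting score has already moved with allocation, a change measured from it can show a group difference that is not a treatment effect, or hide one that is.

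**Working it through.** The plan gives no figure to reproduce on this point. The check is one of order and of days.

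**1. Is there a PSQI before allocation?** Following the form through the schedule:

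| Time | PSQI listed? | Source |
|---|---|---|
| Visit 1 | No | 3.5, 9.13 |
| Final run-in week | No | 5.2.2, 9.13 |
| Visit 3, among forms for randomized participants | Yes, both sequences | 6.2.2, 7.2.2, 9.13 |
| Week 7 of each phase | Yes, both sequences | 6.3.2, 6.5.2, 6.7.2, 7.3.2, 7.5.2, 7.7.2 |

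The Visit 3 form is therefore the only one before Phase 1.

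**2. Does the participant then know the sequence?** No blinding is described. Everyone uses PF in Phase 2, so a participant told SAM for Phase 1 must be in escalation, and one told DSS must be in de-escalation. The Phase 1 mode identifies the whole sequence.

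**3. When does the run-in return window close?** Let run-in last L days and let the forms be sent after day L − 7 + k, where k = 0 to 6 covers the seven possible days of the final week.

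Due day = (L − 7 + k) + 7 = L + k, which is k days after run-in ends.

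| Run-in length | Sent after day | Due on day | Days past end of run-in |
|---|---|---|---|
| 14 days | 7 to 13 | 14 to 20 | 0 to 6 |
| 28 days | 21 to 27 | 28 to 34 | 0 to 6 |

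**4. Does that reach past randomization?** Let g be the number of days from the end of run-in to Visit 3. The plan does not state g, so it is an assumption and the range is shown.

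Permitted overlap = max(0, k − g) days.

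- g = 0: overlap of 0 to 6 days; six of the seven sending days (k = 1 to 6) allow a return after randomization.
- g = 3: overlap of 0 to 3 days; three of the seven (k = 4 to 6) do.
- g = 6 or more: no overlap within the window.

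**5. Comparison with the plan's practice inside the phases.** Those forms have fixed sending days. Week 7: day 42 + 7 = 49. Week 8: day 49 + 7 = 56 = 8 × 7, the end of the minimum 8-week phase. The run-in set has the same 1-week window but no fixed day.

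**6. Which analyses use these starting scores?** The primary outcome is computed from CGM recordings and uses no questionnaire. Whether PF and DSS improve sleep can also be examined within participant from the week-7 PSQI under SAM, PF and DSS, without the Visit 3 score. What remains exposed is the questionnaire analysis in 14.5 where it uses a starting score.

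**The case against.** The strongest reply is that little depends on the Visit 3 score. Section 14.5 does not name the PSQI and does not define a change-from-baseline quantity. The within-participant comparison needs only the week-7 forms. The escalation versus de-escalation contrast is declared unpowered. All of this stands and is why the point is minor.

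Recall also matters. A PSQI completed at Visit 3 asks about a month that lies essentially before allocation, so any shift must come from how that month is reported. This stands too.

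For the run-in forms, a reader may assume that staff would send them on the first day of the week, as they do inside the phases. Then k = 0 and nothing is due after run-in ends. That is plausible, but 5.2.2 does not say it. Late return is permitted by the text, not planned by it.

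A reader might infer three stronger points that the documents do not support:

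- **That the PSQI timing contradicts 1.3.4.** That section sets baseline before system use, not before randomization, and Visit 3 precedes home use of the allocated mode.
- **That these four scores enter the glycemic models as baseline covariates under 1.3.6.** That section separates fixed baseline traits from constructs the intervention can change, which are handled as within-subject covariates. Fear of hypoglycemia is its own example; distress, avoidance and sleep are also re-measured in each phase and fit that class.
- **That the de-escalation PSQI is certainly completed after DSS training.** Section order suggests it, but 7.2 is not strictly chronological: it describes the EMA surveys, which run through the phase, before the initiation forms.

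**Conclusion.** The point holds as a minor one. The only PSQI before Phase 1 is placed among forms for participants already randomized, in both sequences, so it can be influenced by knowledge of allocation. The run-in distress, fear and avoidance forms may be returned 0 to 6 days after run-in ends; whether that falls after randomization depends on the sending day and on the gap to Visit 3, neither of which is stated.

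This rests on two readings. The first is that the wording and placement of 6.2.2 and 7.2.2 mean the participant knows the sequence when the PSQI is completed; no sentence says exactly when it is disclosed. The second is that 14.5 will use these scores as starting points.

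The size and direction of any shift cannot be derived from the documents, and for the PSQI the 1-month recall limits it. The effect is confined to secondary questionnaire analyses, mainly Phase 1 SAM versus DSS. The primary coefficient of variation, the within-participant week-7 PSQI comparison and the Visit 1 questionnaires are unaffected. No sample-size figure changes.

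**What to change.** - In 5.2.2, add the PSQI to the run-in set for both sequences and remove it from 6.2.2 and 7.2.2.
- In 5.2.2, fix the sending day as the first day of the final run-in week, matching the fixed-day practice in the phases. The 1-week window then closes when run-in ends.
- In 5.3.1, add that these four forms are collected before the allocation is disclosed.
- Update 9.13 to match.
- Leave Technology Expectations and INSPIRE at Visit 3, because they concern the system the participant is about to use.

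No form is added. The cost is one form moved by about a week, one extra line in the Visit 3 check, and an occasional short delay at that visit while an outstanding form is completed. The PSQI recall month moves back by about a week, equally in both sequences. An uncontaminated starting score cannot be recovered at analysis, so the change has to be made in the schedule.

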- 447

448 Each modality of treatment will be assessed using the last 4 weeks of CGM recordings, as we
449 expect most of the GV benefits of each intervention to be realized within the first 4 weeks of the
450 intervention, and a minimum of 24 days of data is considered optimal for CGM-based CV
451 determination.

452 1.3.2. Glucose Variability Reduction Achieved with CGM-based expert systems

453 General linear models (GLM) (repeated measures ANOVA) will be used to assess the significance
454 of the differences in average response between SAM, PF, and DSS across appropriate CGM-based
455 metrics. The particular design of the clinical study allow for Aims 1.1, 1.2, and 1.3 to each be
456 addressed independently in a randomized crossover analysis, as shown in Figure 4. While the
457 randomized order of the interventions (escalation vs de-escalation) allows for an objective
458 assessment of the average efficacy of each of them, we will introduce the order as a fixed factor
459 to verify if significant study effects can be detected. Finally, we will study the evolution of GV
460 within each modality period: GV and other CGM-based outcomes will be computed bi-weekly
461 (the minimum length of time for precise GV assessment) and entered in a repeated measures
462 GLM analysis; within-subject contrast (linear and polynomial) using 5 repeated measures per
463 condition to explore the evolution of the glycemic outcomes in time; Aim 1.3.

464
465

Figure 4: Multiple analyses enabled by study design to address Aim 1.1, 1.2 and 1.3

CLINICAL PROTOCOL

466 **1.3.3. Exploration of the effect of treatment escalation vs. de-escalation**

467 A key advantage of the proposed study design (beyond the optimal statistical power) is the
468 possibility to explore the glucose control and psycho-behavioral impact of features being added
469 and/or enhanced with prescriptive components (DSS), vs. features being limited to information
470 (PF) or even removed (SAM). We will perform this analysis by looking at the between factors in
471 the repeated ANOVA analysis, contrasting the escalation group vs. de-escalation group. While
472 not powered, this analysis will provide key insights in the future feature adaptation schemes
473 based on the ATI.

474 **1.3.4. Psychological and Behavioral Questionnaires**

475 As part of Aim 2, we will conduct robust psychosocial analyses of factors important to participant

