766 to contact study staff for a replacement of the meter, test strips, and control solution if a meter
767 fails QC testing at home.

768 Subjects will be instructed to perform blood ketone testing per the Glycemic Treatment
769 Guidelines located in the study training manual.

770 **4.2. Ecological Momentary Assessment Training**

771 After randomization, all participants will be trained on how to access and complete EMAs from
772 their study phone, how to postpone alerts, and enter a voluntary diary. Participants will be
773 informed when the EMAs are scheduled during each phase of the trial.

774 **4.3. Glucagon Emergency Kit**

775 A home glucagon emergency kit will be required. Participants who currently do not have one will
776 be given a prescription for the glucagon emergency kit.

777 **Chapter 5 Study Procedures**

778 **5.1. Study Contacts**

779 **5.1.1. Study Support**

780 Participants will also receive study staff contact information to ask any questions they may have
781 during the study. Additionally, participants will be provided with study contact information for
782 technical support with DiAs System, the study insulin pump and the study CGM. The participant
783 will be asked to call the study team at any time during the study for any health-related issues
784 (adverse events), including hypoglycemia <54 mg/dL, frequent highs >300 mg/dL, or ketones ≥3.0
785 mmol/L. The participant may use the study pump and study CGM during periods of DiAs
786 disconnections or technical difficulties.

787 **5.1.2. Web Conferencing**

788 Study visits may be completed using HIPAA compliant web conference tool. The study team will
789 provide the participant with the meeting information in advance of the appointment.

790 **5.2. Sensor-Augmented Mode (SAM) Run-in Period**

791 **5.2.1. CGM use**

792 Once all training activities are completed, the participant will be given adequate supplies to
793 complete the Run-in home use of the DiAs system in SAM.

794 Participants will complete a minimum of 14 days (if CGM use within the preceding 3 months) or
795 4 weeks (if no CGM use within the preceding 3 months) of home use of the DiAs system in SAM.
796 The study physician may request an additional run-in period of 2 weeks.

797 The participant will be informed that in order to be eligible for the study, the DiAs system in SAM
798 must be used on a minimum of 11 out of 14 days for CGM users or 22 out of 28 days CGM
799 nonusers.

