836 Once all training activities are completed, the participant will be given adequate supplies and
837 study devices to last until the subsequent clinic visit. An appointment for Visit 4 will be scheduled

838 **6.3. Home Use of DiAs in Phase 1 Mode**

839 The participant will complete a minimum of 8 weeks of DiAs use in Phase 1 Mode at home. During
840 the course of Phase 1, participants will complete EMA surveys and post-phase questionnaires.

841 **6.3.1. Phase 1 EMA Surveys**

842 Over the course of 2-3 days every two weeks of Phase 1, the participant will be asked to complete
843 a “Daily Diary” with 3-5 entries of 3-4 questions each day, for a minimum total of 48 entries per
844 participant during each Phase.

845 **6.3.2. Post-Phase 1 Questionnaires Week 7**

846 Participants randomized to escalation will be sent the following questionnaires on week 7 (day
847 42 of Phase 1) and will be asked to complete them within 1 week:

- 848 • Pittsburgh Sleep Quality Index

CLINICAL PROTOCOL

- 849
- Hyperglycemia Avoidance Scale

850 **6.3.3. Post-Phase 1 Questionnaires Week 8**

851 Participants randomized to escalation will sent the following questionnaires on week 8 (day 49
852 of Phase 1) and will be asked to complete them within 1 week:

- 853
- Confidence in Diabetes Self-Care Scale
- 854
- T1-Diabetes Distress Scale
- 855
- Hypoglycemia Fear Survey

856 **6.4. Visit 4 – Phase 2 Initiation**

857 All participants in each randomization scheme use PF in Phase 2. Phase 2 initiation may be
858 conducted either via web conference or an office visit. The participant will remotely receive a
859 mode change for Phase 2. Study staff will review the features of the Personalized Feedback (PF)
860 mode and answer any questions. Participant will have a blood/urine pregnancy test that must be
861 negative in order to continue to participate in this study.

862 **6.4.1. Training on Phase 2 DiAs Mode**

863 The participant will be trained on the following features of the Personalized Feedback System:

- 864
- **Tracking of estimated HbA1c:** When properly calibrated, eA1c is within 0.3% of
865 reference HbA1c on average, and within 1% of HbA1c >95% of the time.
- 866
- **Hypoglycemia Risk Indicator:** Provides an indication of the current risk for
867 hypoglycemia.
- 868
- **Insulin Sensitivity Profile & Indicator:** Tracks changes in insulin sensitivity (SI) and
869 creates daily and monthly SI profiles.
- 870

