- **Insulin on Board:** Tracks active insulin to avoid insulin stacking using a common 4-6 hour
871 action curve.
- 872
- **Personalized weekly feedback.** Provides advice to the user on what went well in terms
873 of glycemic control and system use in the past week and what may be a good thing to
874 focus on for the following week.

875 **6.4.2. Phase 2 Initiation Questionnaires**

876 Participants randomized to escalation will complete the following questionnaires:

- 877
- Technology Expectations (burdens subscale only)
- 878
- INSPIRE (revised for DSS)

CLINICAL PROTOCOL

879 **6.4.3. Adverse Event Assessment**

880 The participant will be asked about any of adverse events, adverse device effects, and device
881 issues since the last visit. The participant will also be asked if there were any low BGs <54 mg/dL,
882 high BGs >300 mg/dL, or ketones ≥ 3.0 mmol/L since the last visit.

883 Once all training activities are completed, the participant will be given adequate supplies and
884 study devices to last until the subsequent clinic visit. An appointment for Visit 5 will be scheduled.
885 Participants will be encouraged to contact the study team between visits as needed (i.e. report
886 adverse events in real-time).

887 **6.5. Home Use of DiAs in Phase 2 Mode**

888 The participant will complete a minimum of 8 weeks of DiAs use in Phase 2 Mode at home.

889 During the course of Phase 2, participants will complete EMA surveys and post-phase
890 questionnaires.

891 **6.5.1. Phase 2 EMA Surveys**

892 Over the course of 2-3 days every two weeks of Phase 2, the participant will be asked to complete
893 a "Daily Diary" with 3-5 entries of 3-4 questions each day, for a minimum total of 48 entries per
894 participant during each Phase.

895 **6.5.2. Post-Phase 2 Questionnaires Week 7**

896 All participants will be sent the following questionnaires on week 7 (day 42 of Phase 2) and will
897 be asked to complete them within 1 week:

- 898 • Technology Acceptance (burdens subscale only)
- 899 • Pittsburgh Sleep Quality Index
- 900 • T1-Diabetes Distress Scale

901 **6.5.3. Post-Phase 2 Questionnaires Week 8**

902 All participants will be sent the following questionnaires on week 8 (day 49 of Phase 2) and will
903 be asked to complete them within 1 week:

- 904 • Hypoglycemia Fear Survey
- 905 • Hyperglycemia Avoidance Scale
- 906 • Confidence in Diabetes Self-Care Scale

CLINICAL PROTOCOL

907 **6.6. Visit 5 – Phase 3 Initiation**

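### The sleep questionnaire recalls one month but is sent on day 42, so 30-53% of recalled days fall in the first 4 weeks that the CGM analysis leaves out

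*Combined protocol and SAP*

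**What the plan says.** Section 9.9 gives the purpose of the PSQI: "This questionnaire will be used to assess whether the PF and DSS improve sleep quality and" quantity. It describes an instrument that rates sleep "quality over a 1-month time interval".

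The form goes out in week 7 of every phase in both sequences (sections 6.3.2, 6.5.2, 6.7.2, 7.3.2, 7.5.2 and 7.7.2, and the table in 9.13). For Phase 2, section 6.5.2 reads: "All participants will be sent the following questionnaires on week 7 (day 42 of Phase 2) and will". For Phase 1 of de-escalation, section 7.3.2 gives "day 42 of Phase 1) and will be asked to complete them within 1 week". Phase length is a minimum, as in section 6.3: "The participant will complete a minimum of 8 weeks of DiAs use in Phase 1 Mode at home".

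Sections 1.3.1 and 14.3.1 assess each modality on its last 4 weeks of CGM data, because the investigators "expect most of the GV benefits of each intervention to be realized within the first 4 weeks of the" intervention and because at least 24 days of data are considered optimal for CV. Section 1.3.4 places the questionnaire battery at baseline and after each modality. Section 14.5 plans general linear models of questionnaire scores over time and of their association with glycemic outcomes. It does not name the PSQI and gives no rule on recall windows.

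**The concern.** An instrument with a one-month recall, completed at the end of an 8-week phase, would describe almost exactly the 4 weeks used for the glycemic outcome. Sent two weeks before the end, it describes an earlier month, although the plan places questionnaires after each modality and heads these sections as post-phase.

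Two things are at stake. First, any model under 14.5 that relates sleep to CGM outcomes would pair measurements from different, only partly overlapping months. This needs no assumption about how sleep behaves. Second, if sleep responds gradually to a new mode, the score includes days on which the response is incomplete, and the PF-SAM and DSS-SAM sleep differences may come out too small. This second effect is conditional.

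**Working it through.** The plan states no overlap figure to reproduce. Its calendar is consistent: week 7 starts after 6 x 7 = 42 days, week 8 after 7 x 7 = 49, an 8-week phase ends on day 56, and its last 4 weeks are days 29-56.

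**Inputs.** Recall length r = 30 days (assumption; section 9.9 says one month without a day count). Completion day c from 42 to 49 (week-7 sections). Phase length 56 days (section 6.3 and its counterparts). CGM outcome window days 29-56 (1.3.1, 14.3.1).

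**Formulas**, counting the completion day as the last recalled day:
- recalled days: c - r + 1 to c
- recalled days within days 1-28: 28 - c + r
- outcome days covered: c - 28
- phase days after the recall ends: 56 - c

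| Completed on | Recalled days | In first 4 weeks | Outcome days covered | Phase days missed at end |
|---|---|---|---|---|
| day 42 | 13-42 | 16/30 = 53% | 14 of 28 | 14 |
| day 49 | 20-49 | 9/30 = 30% | 21 of 28 | 7 |
| day 56 (for comparison) | 27-56 | 2/30 = 7% | 28 of 28 | 0 |

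**Other month lengths.** With r = 28 the share is 14/28 = 50% on day 42 and 7/28 = 25% on day 49. With r = 31 it is 17/31 = 55% and 10/31 = 32%. The outcome days covered do not change.

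**Longer phases.** Eight weeks is a minimum. If a phase ran 9 weeks and the CGM window moved to its last 4 weeks, the days left out would run to day 35, and the share would be 23/30 = 77% on day 42 and 16/30 = 53% on day 49.

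**Days from the previous mode.** Even with r = 31 and c = 42, recall starts on day 42 - 31 + 1 = 12 of the current phase, so none.

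**Possible dilution.** The documents give no onset time for sleep, so these are scenarios:
- Immediate response: no loss.
- Linear rise over 28 days: the shortfall on day t is 1 - t/28. Completed on day 42, the sum over days 13-28 is (15 + 14 + ... + 0)/28 = 120/28 = 4.29 days, or 4.29/30 = 14%. As a continuous area it is 16²/(2 x 28)/30 = 15%. Completed on day 49, it is (36/28)/30 = 4%, or 9²/(2 x 28)/30 = 5% as an area. The range is about 4-15%.
- No response until day 28, then full: the loss equals the share itself, 30-53%. Nothing in the documents points to this; it is an outer bound.

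These percentages apply to the step from the preceding mode to the current one, so their effect on a given contrast depends on the sequence. They do not apply to Phase 1 of escalation, where participants continue SAM after a SAM run-in and no mode change occurs.

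**The case against.** The best counter-argument is that the 4-week exclusion concerns CGM only. Both stated reasons, the expected timing of the GV benefit and the days needed for CV, have nothing to do with sleep. A reader might infer that the plan treats weeks 1-4 as a transition period for every outcome. It does not: no section calls them a transition, and none sets a lead-in for questionnaires. A reader might also infer that the score mixes in sleep under the previous mode. It does not, since every recalled day lies within the current mode. Dilution is therefore possible but not shown. Week-7 timing is also the same for all three modes.

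A further tempting inference is that the Visit 3 PSQI is faulty, because after a 14-day run-in 16 of 30 recalled days precede SAM. Section 1.3.4 describes the baseline battery as taken before system use, so such days fit its purpose. After the 4-week run-in of section 5.2.1, only about 2 of 30 days precede SAM.

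The EMA diary also asks two sleep items, so late-phase sleep is not unmeasured. It does so on only 2-3 days every two weeks, which is partial backup and not a substitute for the PSQI. Finally, the PSQI is not primary, and no stated alpha or power depends on it.

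All of this stands, and it limits what can be claimed about bias. It leaves the mismatch between the sleep month and the CGM month untouched.

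**Conclusion.** The misalignment is real and follows from the plan's own dates. With a 30-day month, 30-53% of recalled days fall in weeks 1-4 of the mode, 14-21 of the 28 CGM outcome days are covered, and the last 1-2 weeks of an 8-week phase go unrecalled. This rests only on the month length and on completion within the allowed week. Understated sleep differences are a possibility: none with an immediate response, about 4-15% of the step from the preceding mode under an assumed linear 28-day onset, and not applicable to escalation Phase 1. The primary analysis is unaffected. This is a cheap improvement to a secondary measure, of low to moderate priority.

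**What to change.** Exchange the PSQI with the Confidence in Diabetes Self-Care Scale. The PSQI then goes out in the existing week-8 mailing (day 49), to be completed as near as possible to the end of week 8 and before the mode change or device return. For completion on days 49-56, the share of recalled days in weeks 1-4 falls to 30% down to 7%, and 21 to 28 of the 28 outcome days are covered. Encouraging completion near day 56 matters, because a form filled in on day 49 gains nothing over the latest completion allowed now.

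Edit 6.3.2/6.3.3, 6.5.2/6.5.3, 6.7.2/6.7.3, 7.3.2/7.3.3, 7.5.2/7.5.3, 7.7.2/7.7.3 and table 9.13 together. In the same edit, reconcile the Phase 3 text of 6.7.2, 7.7.2 and 7.7.3, which counts its days from Phase 1 (6.7.2: "42 of Phase 1) and will be asked to complete them within 1 week"). Introduce the change at the start of a cohort, so that each participant has the same timing in all three phases.

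The cost is a minor amendment, and the Confidence scale is collected one week earlier. Section 9.4 states no recall period for that scale, so little should be lost. The burden is about equal (5-10 minutes for the PSQI, 10 for the Confidence scale), with no added items, visits or staff. If the timing is kept, the plan should at least justify the different window.
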